3.1. Eligibility Criteria

- 3.1.1. Patient has platinum-sensitive, recurrent ovarian, fallopian-tube or peritoneal cancer. Platinum sensitivity is defined as complete clinical remission after frontline chemotherapy lasting greater than 6 months
- ^{3.1.2.} Patient has completed at least 2 courses of platinum-based chemotherapy with a PR or CR as defined by the Response Evaluation Criteria in Solid Tumors (RECIST) v1.1³⁹ or a CA-125 response, according to Gynecological Cancer InterGroup (GCIG) criteria⁴⁰
- 3.1.3. BRCA testing required (results not needed for registration)
- 3.1.4. Age ≥ 18 years old
- 3.1.5. ECOG performance status score of 0, 1, or 2 (See Appendix A)
- 3.1.6. Life expectancy greater than 6 months
- 3.1.7. Normal organ and marrow function as defined below:
 - Absolute neutrophil count (ANC) \ge 1.5 x 10⁹/L
 - Platelets $\geq 100 \text{ x } 10^9/\text{L}$
 - Hemoglobin (Hgb) \geq 8 g/dL (blood transfusions to reach this amount are allowed)

- Serum creatinine $\leq 1.5 \text{ mg/dL}$
- Total serum bilirubin $\leq 1.5 \text{ x ULN}$

-AST and ALT \leq 2.5 x ULN

- 3.1.8. Able to take oral medication
- 3.1.9. Not pregnant and not breastfeeding
- 3.1.10. Able to understand and willingness to sign a written informed consent document
- 3.1.11. Patients must be enrolled within 8 weeks of completing last cycle of chemotherapy

3.2 Exclusion Criteria

- 3.2.1 Patient has had a prior invasive malignancy diagnosed within the last five years (except [1] non-melanoma skin cancer or [2] prior in situ carcinoma of the cervix or breast [3] has been without evidence of invasive disease for greater than 3 years)
- 3.2.2 Patients receiving any other investigational agents
- 3.2.3 History of allergic reactions attributed to compounds of similar chemical or biologic composition to olaparib
- 3.2.4 Uncontrolled intercurrent illness that could affect their participation in the study including, but not limited to, ongoing or active infection; symptomatic congestive heart failure; unstable angina pectoris; cardiac arrhythmia; known inadequately controlled hypertension; significant pulmonary disease including dyspnea at rest, patients requiring supplemental oxygen, or poor pulmonary reserve; or psychiatric illness/social situations that would limit compliance with study requirements
- 3.2.5 Impairment of gastrointestinal function or disease that may significantly alter the absorption of olaparib
- 3.2.6 Patients who have received prior treatment with a PARP inhibitor
- 3.2.7 History of noncompliance to medical regimens

3.3 Inclusion of Women and Minorities

This clinical trial will not exclude potential subjects from participating in this or any study solely on the basis of ethnic origin or socioeconomic status. Every attempt will be made to enter all eligible patients in this protocol to address the study objectives in a population representative of the entire ovarian cancer population. (See Planned Enrollment Table in Section 13.2)

4. SUBJECT SCREENING AND REGISTRATION PROCEDURES

Subjects will be identified in the outpatient clinic. After informed consent is obtained, all patients satisfying the inclusion/exclusion criteria must have eligibility confirmed by the Clinical Trials

Office. The patient will not be considered registered and enrolled in the study until all information is confirmed by the Clinical Trials Office of Research Staff. To enroll a patient, contact the Gyn/Onc Research group Monday through Friday, 8:00AM-4:00PM.

5. SURVEILLANCE MONITORING PLAN

This is a single-arm, open-label phase II clinical trial evaluating delayed start olaparib maintenance therapy, based on a rise in CA125, for patients with epithelial ovarian cancer who have had a partial or complete response to platinum-based treatment. Patients will be enrolled within 8 weeks of completing platinum-based therapy for recurrent disease. At the time of enrollment, patients will be monitored with CA125 levels every 28 days.

At the first evidence of a two-fold rise in CA125 from baseline, patients will undergo a CT scan to evaluate for any visible lesions, including new lesions for those with CR and new, persistent or progressive lesions for those with PR to most recent therapy, and then will be started on olaparib therapy. In the setting of new or progressive lesions, patients will be followed per protocol. Patients may undergo CT imaging prior to rise in CA-125 at the discretion of the treating physician for patient symptoms. Eighty-one patients will be enrolled through UPMC medical and gynecologic oncology offices.

6. TREATMENT PLAN

As noted above, at first evidence of two-fold rise in CA125, patients will undergo a CT scan to evaluate for any visible lesions and then will be started on olaparib therapy.

The trial will involve the optional collection of tumor samples at enrollment (archival tissue) and at the time of recurrence or progression, if biopsies are obtained as part of standard of care, to understand the PARP-I resistance mechanisms.

6.1. Agent Administration

Olaparib treatment will be started when CA125 rises by two-fold of their nadir value. Olaparib will be dosed at 300 mg orally twice a day. Twenty-eight days of treatment will be considered one cycle. Patients will be required to maintain a medication diary (See Appendix B).

Patients starting olaparib will continue treatment until disease progression, per RECIST v1.1³⁹ or intolerable toxicity, defined as any grade 3 or 4 adverse event, per National Cancer Institute's Common Terminology Criteria for Adverse Events (CTCAE) v5.0 or Patient Reported Outcomes-Common Terminology Criteria for Adverse Events (PRO-CTCAE), that does not resolve completely or to grade 1 within 28 days after onset. Patients removed from study for unacceptable adverse event(s) will be followed closely until resolution or stabilization of the adverse event (at least 30 days).

Olaparib is FDA-approved for maintenance therapy for patients with platinum sensitive recurrent epithelial ovarian cancer with a complete or partial response to most recent platinum based chemotherapy. Therefore, drug will be covered by standard insurance. Additionally, after discussion with The UPMC Health Plan, they will approve treatment after 2 prior lines even with the delay in standard start time defined by the maintenance indication.

Treatment will be administered on an outpatient basis. Appropriate dose modifications are described in Section 7. No other investigational or commercial agents or therapies may be administered with the intent to treat the patient's malignancy.

Reported adverse events and potential risks are described in Section 7.

6.2. General Concomitant Medication and Supportive Care Guidelines

6.2.1. Concomitant Therapy:

Patients must be instructed not to take any additional medications (including over-the-counter products) during the trial without prior consultation with the investigator. The investigator should instruct the patient to notify the study site about any new medications he/she takes after the start of study drug. All medications (other than study drug) and significant non-drug therapies (including physical therapy and blood transfusions) taken within 28 days of starting study treatment through the 30-day safety follow up visit should be reported on the Case Report Form. If concomitant therapy must be added or changed, the reason and name of the drug/therapy will be recorded.

In general, the use of any concomitant medication/therapies deemed necessary for the care of the patient are allowed, including drugs given prophylactically (e.g. antiemetics +/- steroids), with the following exceptions:

- No other investigational therapy will be given to patients.
- No anticancer agents other than the study medication administered as part of this study protocol should be given to patients. If such agents are required for a patient then the patient must first be withdrawn from the study.
- Leukocyte growth factors (e.g., G-CSF and GM-CSF) are not to be administered systematically but may be prescribed by the investigator for severe neutropenia if this is thought to be appropriate.
- No live vaccines will be administered to patient due to immunosuppressant potential of olaparib.

Drugs or substances known to be inhibitors or inducers of the isoenzyme CYP3A should be avoided in association with olaparib as these can alter drug metabolism. Strong inhibitors or inducers of the isoenzyme CYP3A should not be administered as systemic therapy and should be avoided whenever possible (See Appendix C). Investigators should consult a frequently updated drug information reference for a list of strong inducers and inhibitors.

- **CYP3A inhibitors:** Avoid concomitant use with moderate or strong CYP3A inhibitors (consider alternative agents with less CYP3A inhibition). If co-administration with a **moderate** CYP3A inhibitor cannot be avoided, reduce dose to 150 mg twice daily. If co-administration with a **strong** CYP3A inhibitor cannot be avoided, reduce dose to 100 mg twice daily.
- **CYP3A inducers:** Avoid concomitant use with moderate or strong CYP3A4 inducers; a potential for reduced olaparib efficacy exists if moderate CYP3A inducers cannot be avoided.

6.2.2. Supportive care

No routine prophylactic medications are indicated at the start of therapy. In general, the use of any concomitant medication/therapies deemed necessary for the care of the patient are allowed with the exceptions noted in 6.2.1

6.3. **Duration of Therapy**

Patients will be enrolled continuously to the study. Patients will continue evaluation and treatment until one of the following criteria applies:

- Disease progression per RECIST v1.1³⁹
- Unacceptable adverse event(s) defined as any grade 3 or 4 adverse event, per National Cancer Institute's Common Terminology Criteria for Adverse Events (CTCAE) v5.0 or PRO-CTCAE, that does not resolve to grade ≤ 1 within 28 days after onset.
 - Treatment will be interrupted for any grade 3 or 4 event related to treatment. If the toxicity resolves entirely or to grade 1, treatment will be restarted with a dose reduction. If the event does not resolve within 4 weeks or if two previous treatment interruptions with subsequent dose reductions occur, the patient will be withdrawn.
- Patient withdraws consent.
- Development of second malignancy (except for basal cell carcinoma or squamous cell carcinoma of the skin) that requires treatment, which would interfere with this study.
- Intercurrent illness that prevents further administration of treatment
- General or specific changes in the patient's condition render the patient unacceptable for further treatment in the judgment of the investigator.

6.4. **Duration of Follow Up**

Patients will be followed until the initiation of the next therapy post olaparib treatment. Each patient, regardless of reason for removal from study, will have at least 18 months follow up relative to time of enrollment. Secondary efficacy endpoints will be tracked after official follow-up has been completed.

Assessments in follow up:

- Office visit or review of medical records every 3 months
- Survival endpoints both progression free survival (PFS) and overall survival (OS)

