6.5. Criteria for Removal from Study

Patients will be removed from treatment when any of the criteria listed in Section 6.3 apply or once they have completed follow-up as described in Section 6.4. The reasons for treatment discontinuation and study removal and the associated dates must be documented in the Case Report Form.

Patients can be taken off study at any time at their own request, or they may be withdrawn at the discretion of the investigator for safety, behavioral, or administrative reasons. The reason(s) for discontinuation from study will be documented and may include:

- Patient withdraws consent (termination of treatment and follow-up);
- Loss of ability to freely provide consent through imprisonment or involuntary incarceration for treatment;
- Patient is unable to comply with protocol requirements;

- Treating physician judges continuation on the study would not be in the patient's best interest;
- Patient becomes pregnant (pregnancy to be reported along same timelines as a serious adverse event);
- Development of second malignancy (except for basal cell carcinoma or squamous cell carcinoma of the skin) that requires treatment, which would interfere with this study;
- Lost to follow-up: if a research subject cannot be located to document PFS after 6 months, the subject will be considered "lost to follow up"
- Termination of the study by the University of Pittsburgh Medical Center
- Patient completes protocol treatment and follow-up criteria.

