7.1. Hematologic Toxicity

	Dose may be reduced to 200 mg PO BID if recurs at reduced dose, but if recurs for a third time, treatment
	should be discontinued.
Grade 3 (≥25 x 10 ⁹ /L - <50 x 10 ⁹ /L)	Dose interruption until recovery to grade ≤ 1 .
	Monitor platelets weekly until recovery.
	If resolves to grade ≤ 1 within 28 days, resume at reduced
	dose 250 mg PO BID.
	Dose may be reduced to 200 mg PO BID if recurs at
	reduced dose, but if recurs for a third time, treatment
	should be discontinued.
Grade 4 (<25 x 10 ⁹ /L)	Dose interruption until recovery to grade ≤ 1
	Monitor platelets weekly until recovery.
	If resolves to grade ≤ 1 within 28 days, resume at reduced
	dose 250 mg PO BID.
	Dose may be reduced to 200 mg PO BID if recurs at reduced dose, but if recurs for a third time, treatment
	should be discontinued.
Absolute neutrophil count (ANC)	should be discontinued.
Grade 1 (\geq 1.5 x 10 ⁹ /L)	No dose adjustment required.
Grade 2 ($\geq 1.0 - \langle 1.5 \times 10^{9}/L \rangle$)	No dose adjustment required.
Grade 3 ($\geq 0.5 - <1.0 \times 10^{9}/L$)	Dose interruption until recovery to $\geq 1.0 \times 10^{9}$ /L. If
	resolves to grade ≤ 1 within 28 days, resume at reduced
	dose 250 mg PO BID.
	Dose may be reduced to 200 mg PO BID if recurs at
	reduced dose, but if recurs for a third time, treatment
	should be discontinued.
Grade 4 (<0.5 x 10 ⁹ /L)	Dose interruption until recovery to $\geq 1.0 \text{ x } 10^9/\text{L}$. Re-
	initiate olaparib at 250 mg PO BID. If toxicity recurs at
	grade 4: temporary dose interruption until recovery to
	$\geq 1.0 \text{ x } 10^9/\text{L and r}$
Febrile neutropenia	
Grade 3 ANC $<1.0 \times 10^9$ /L with a	Dose interruption until improvement of ANC $\geq 1.0 \times 10^{9}$ /L
single temperature of >38.3 °C (101	and no fever. Restart with dose reduction of 250 mg PO
°F) or a sustained temperature of \geq 38 °C (100.4 °F) for more than one hour	BID. If febrile neutropenia recurs, discontinue olaparib.
Grade 4 Life-threatening	Discontinue olaparib
consequences; urgent intervention	
indicated	
multated	

Treatment-related anemia may be managed by transfusions without interruption of treatment Any hematologic AE that does not resolve to grade ≤ 1 within 28 days despite maximum supportive care remove from study.

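### Section 6.3 restarts olaparib after any resolved related grade 3–4 toxicity, Section 7 orders a permanent stop for four such event types, and nothing says which section governs

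*Combined protocol and SAP*

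**What the plan says.** Section 6.3 (Duration of Therapy) sets a general rule for toxicity. It opens with "Treatment will be interrupted for any grade 3 or 4 event related to treatment" and continues: "If the toxicity resolves entirely or to grade 1, treatment will be restarted with a dose reduction". Withdrawal follows in two situations only. One is failure to resolve within 4 weeks. The other is the cap: "if two previous treatment interruptions with subsequent dose reductions occur, the patient will be withdrawn". The text does not say whether the two interruptions are counted across all toxicities or for each toxicity separately, and it exempts no toxicity from the restart.

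Section 7 gives toxicity-specific rules, and some end treatment outright:

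- In the febrile neutropenia rows of 7.1, the grade 4 instruction is to "discontinue olaparib", with no restart. The grade 3 row allows one restart and then says: "If febrile neutropenia recurs, discontinue olaparib".
- The general table in 7.2 stops the drug when a non-hematologic toxicity that was grade 3 returns at grade 3, and likewise when one that was grade 4 returns at grade 4.
- Section 7.2.6 stops the drug once pneumonitis is confirmed.

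Two cross-references bear on which section prevails. Section 6.1 says: "Appropriate dose modifications are described in Section 7". Section 6.5 says: "Patients will be removed from treatment when any of the criteria listed in Section 6.3 apply".

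**The concern.** For the same patient and the same event, the two sections can give opposite instructions. A related grade 3 or 4 event that has resolved in time, in a patient with fewer than two earlier interruptions, leads to a restart at a lower dose under 6.3 and to a permanent stop under Section 7. The restart in 6.3 is worded as something that will happen, not as an option.

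What is at stake is patient safety and uniform conduct. An investigator who follows 6.3 as written would give olaparib again after toxicities that Section 7 treats as the end of treatment. Two investigators could handle identical cases differently, and each could cite the protocol.

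**Working it through.** No sample size, power or error rate is involved, so the check is a comparison of rules followed by a rough count.

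**Step 1. Restarts allowed under each section.** Take a patient with no earlier interruption whose event is related, grade 3 or 4, and resolved to grade 1 or better within 4 weeks. Section 6.3 withdraws the patient once two interruptions with reductions have already occurred, so it allows up to 2 restarts. For this patient the figure is the same whether the cap is pooled or per toxicity. If the cap is pooled and partly used by another toxicity, fewer remain.

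| Event | Restarts under 6.3 | Restarts under Section 7 | Agree? |
|---|---|---|---|
| Febrile neutropenia, grade 4 (7.1) | up to 2 | 0 | No |
| Febrile neutropenia, grade 3, then any recurrence (7.1) | up to 2 | 1 | No |
| Non-hematologic grade 3 or 4, recurring at the same grade (7.2) | up to 2 | 1 | No |
| Confirmed pneumonitis (7.2.6), if related, grade 3–4 and resolved in time | up to 2 | 0 | No |
| Anemia or thrombocytopenia, grade 3–4; ANC, grade 3 (Section 7 and 7.1 tables) | up to 2 | 2, stop at the third occurrence | Yes |

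The last row serves as a control. Where Section 7 allows two reductions and stops at the third occurrence, it matches the 6.3 cap. The disagreement is therefore confined to the events in the first four rows. The count of four treats the grade 3 and grade 4 non-hematologic recurrence lines as one type; counted by line there are five.

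**Step 2. Does any text settle the order?**

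- Section 6.1 sends the reader to Section 7 for dose modifications but does not say that Section 7 overrides 6.3. Its own definition of intolerable toxicity covers only grade 3 or 4 events that fail to resolve, so it does not capture the Section 7 stops.
- Section 6.5 names 6.3 as the source of criteria for removal from treatment and does not mention Section 7. It is not an exclusive list, so it does not forbid a Section 7 stop. It does not require one either.
- The last criterion in 6.3 covers changes in condition that "render the patient unacceptable for further treatment in the judgment of the investigator". This permits a stop but does not mandate it.

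No text states precedence.

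**Step 3. Size.** Inputs: 75 treated patients (the evaluable target in the sample size section) and the olaparib risk list in Section 8.1, assuming its rates apply here. Pneumonitis sits under a heading that combines rates below 1% with postmarketing and case reports; I take it as below 1%.

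- Pneumonitis, any grade: fewer than 0.01 × 75 = 0.75 patients. Cases that are also related, grade 3–4 and resolved within 4 weeks would be fewer still.
- Febrile neutropenia: no rate is given.
- Recurrence of febrile neutropenia or of a non-hematologic grade 3–4 toxicity: no rate is given.

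Only the pneumonitis component can be sized from the documents.

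**The case against.** The strongest reply is that a specific toxicity rule ordinarily refines a general one. The 6.3 sentence sits beneath the definition of an unacceptable adverse event, Section 6.1 directs the reader to Section 7 for dose modifications, and Sections 6.3 and 6.5 both let the investigator take a patient off treatment. An investigator who follows a Section 7 stop therefore has authority to do so. That stands, and it makes actual re-exposure less likely. It does not remove the conflict, because precedence is left to inference and discretion to stop is weaker than an instruction to stop. The Section 7 tables are also headed as recommendations, which makes it easier to treat a stop as optional beside the firm restart in 6.3. The pneumonitis instruction lies outside those tables.

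A reader might also infer that Section 7 is looser than 6.3 in places, so that the conflict runs both ways and reaches many more patients. The documents do not support this:

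- *Anemia.* The 7.1 sentence allowing transfusion without interruption names no grade. The grade 3 and 4 anemia rows require interruption, as 6.3 does, and the closing text of 7.1 calls for interruption in severe hematologic toxicity. The sentence can be read as covering the lower grades.
- *Restart after grade 3 febrile neutropenia.* With ANC at or above 1.0 × 10⁹/L and no fever, the event no longer meets its definition. It can count as entirely resolved, which satisfies 6.3.
- *Grade 4 ANC.* The row is cut off in the available text. Section 7.1 also removes any patient whose hematologic event has not reached grade 1 or better within 28 days.

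Nor does the text support saying that the cap is pooled across toxicities; it leaves this open.

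**Conclusion.** The point holds: the plan is wrong as written, as an internal inconsistency of minor severity. Four event types in Section 7 require a permanent stop where 6.3, taken literally, requires a restart at a reduced dose, and no text says which prevails. For pneumonitis the conflict is limited to related grade 3–4 cases that resolve in time.

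Few patients are expected to be affected. The pneumonitis figure of fewer than 0.75 in 75 rests on the Section 8.1 rate applying to this trial; the size of the rest cannot be computed from the documents. A reader might infer that inconsistent stopping would bias time to next therapy. Nothing in the documents shows this, and no effect on the primary endpoint is claimed. The reason to correct the text is safety: the protocol should not contain a rule that restarts the drug after toxicities it elsewhere treats as final.

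**What to change.** In 6.3, directly after the clause on restarting with a dose reduction, add: *unless Section 7 requires discontinuation for that toxicity, in which case Section 7 governs*. Keep the two-interruption limit as the overall ceiling. In 6.5, cite Section 7 alongside 6.3 as a source of criteria for removal from treatment.

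The clause works whether the cap is pooled or per toxicity, and leaves unchanged the rules on which the two sections already agree. The cost is one clause and one cross-reference in an amendment, with no change to data collection or analysis.

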6.5. Criteria for Removal from Study

Patients will be removed from treatment when any of the criteria listed in Section 6.3 apply or once they have completed follow-up as described in Section 6.4. The reasons for treatment discontinuation and study removal and the associated dates must be documented in the Case Report Form.

Patients can be taken off study at any time at their own request, or they may be withdrawn at the discretion of the investigator for safety, behavioral, or administrative reasons. The reason(s) for discontinuation from study will be documented and may include:

- Patient withdraws consent (termination of treatment and follow-up);
- Loss of ability to freely provide consent through imprisonment or involuntary incarceration for treatment;
- Patient is unable to comply with protocol requirements;

- Treating physician judges continuation on the study would not be in the patient's best interest;
- Patient becomes pregnant (pregnancy to be reported along same timelines as a serious adverse event);
- Development of second malignancy (except for basal cell carcinoma or squamous cell carcinoma of the skin) that requires treatment, which would interfere with this study;
- Lost to follow-up: if a research subject cannot be located to document PFS after 6 months, the subject will be considered "lost to follow up"
- Termination of the study by the University of Pittsburgh Medical Center
- Patient completes protocol treatment and follow-up criteria.

